There are four purposes to this study. The primary purpose of this study is to evaluate the impact of walking as an exercise component of VR on both primary and secondary vestibular-specific outcome measures. The primary outcomes are mCTSIB, TUG test, DGI, and DHI, while the secondary outcomes are the total number of visits and length of interventions (in weeks). The second purpose is to evaluate whether pedometers increase the adherence of older adults with vestibular issues to a walking program. This will be measured by change in physical activity, as represented by International Physical Activity Questionnaire (IPAQ) Walking Metabolic Equivalent of Task (MET)-minutes/week and IPAQ Total Physical Activity MET-minutes/week scores from the IPAQ short form during the episode of care (admission and discharge) and on four-weeks follow-up compared to those patients who only received instructions to walk without a pedometer. The third purpose of this study is to establish test-retest reliability of the TUG test on older adults with dizziness. Lastly, the fourth purpose of this study to investigate if the TUG, DGI, and mCTSIB are significant and strong predictors of the DHI in older adults with dizziness. Protocol #1365169 “Predictors of Disability in the Older Adults” is being performed to supplement the number of subjects for the fourth objective of this study.

Study Design

Research Design

1. Experimental Design. To answer the first and second study objectives, a pragmatic, randomized, prospective, clinical study on 54 older adults with dizziness will be utilized. This will be conducted at Florida Hospital Sports Medicine and Rehabilitation locations that offer vestibular therapy. These are in East Orlando and Winter Park.
2. Correlation Design. A correlation analysis will be performed on the data collected on 54 subjects in the experimental design to establish the test-retest reliability of the Timed Up and Go.
3. Cross-sectional Descriptive Design. A regression analysis will be performed on three predictors of the Dizziness Handicap Inventory, obtained from the data collected on 54 subjects in the experimental design and from Florida Hospital Sports Medicine and Rehabilitation Physical Therapy medical charts from June 2015 to June 2018 that met the inclusion and exclusion criteria that were outlined in the Protocol #1365169.

Study Agent, Device, and/or Intervention Description

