The VRWP group will have VR with an instruction to increase their number of steps daily to at least 3,000 steps using the pedometer (VR plus walking plus pedometer group). They will receive pedometers (Fitbit Zip), instructions on how to use the pedometer, step log forms, with home instruction handout to walk more at least more than ten minutes at a time. This group will be instructed to wear a pedometer on or below the waist such as belt, waistband, or in trousers' pocket, during waking hours, all day, except for bathing or swimming. A clip designed to keep the Fitbit Zip clipped to the clothing will be provided. There is no charging time. Fitbit Zip uses a replaceable watch battery that can last up to 6 months. The participants will record on their activity log the number of steps shown on the step display at the end of the day. The Fitbit Zip will be device inclusive. Subjects will not be given instruction to program their information or synchronize their Fitbit Zip with an application software on a smart phone, tablet, or any computer device. The daily step log form will be given to the research staff every visit for recording. The research staff will encourage their participants to increase their daily steps at least 10% until they achieve at least 3,000 steps daily. The older adults in the group will be trained on how to use the pedometers before they take them home, and will have the opportunity to review this instruction with the research staff on consecutive visits if needed. There may be cost associated with the study in case of lost or malfunction from using the pedometer due to the subject will be encouraged but not required to replace the pedometer. The subject will continue to be the VRWP group and this situation will be reported in the discussion of results.

The VRW group will receive VR and a time-based instruction to walk more daily at least 10 minutes at a time (VR plus walking no pedometer group). This group will be instructed on the benefits of walking (similar to the first group) but will not be given the pedometer. They will have home instruction handouts to walk more at least more than ten minutes at a time and a walking log sheet. The research staff will instruct their participants to increase their daily time at least 10% until they achieve at least 30 minutes of walking exercise daily. The walking log sheet form will be given to the research staff by the participant every visit for recording.

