The VR (control) group will follow the conventional VR physical therapy without the encouragement of walking and without specification of walking in the home exercise program.

The use of an assistive device can be recommended for any subject in any group by the research staff to maximize safety. The patient may need to purchase the assistive device.

Participants who do not belong to the intervention group with pedometer will receive a pedometer after they completed the study. They will receive instructions on how to use the pedometer prior or on the day of their last visit.

Study Visits

For the experimental design that will be conducted at Florida Hospital locations, the following data will be collected as standard of care by the physical therapist during initial evaluation, and if more time is needed, during the first follow-up physical therapy appointment: mCTSIB, TUG, DGI, DHI, age, gender, body mass index, home situation, Functional Comorbidity Index (FCI) total, ability to drive, medications and insurance type. After the subject signs the informed consent, the study coordinator will be notified by the research staff to conduct a retrospective chart review on the physical therapy initial evaluation and first follow-up visit, if applicable, of the subject. The study coordinator will extract the following baseline measurements from the subject's medical record: DGI, mCTSIB, DHI, TUG and socio-demographic data that include age, gender, body mass index, home situation (lives alone or with social support), Functional Comorbidity Index (FCI) total, ability to drive (able or unable), medications for vertigo and insurance type (Medicare/Non-medicare). Based on the retrospective chart review, the study coordinator will determine if the subject is eligible to participate in the study.

Visit 1: Once the study coordinator determined that the subject is eligible to participate in the study, the subject will be assigned a research number and will be randomized into one of the three intervention groups. The research staff can initiate or continue the VR program. For the test-retest reliability of the TUG test, there will be one practice trial followed by two final performances that will be included in the data analysis. The subject will also be asked to complete the IPAQ-short form questionnaire. The test-retest reliability of TUG and the IPAQ-short form questionnaire are for research purposes only.

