The principal investigator may share the research data with accreditation organizations and regulatory agencies, dissertation committee, and publications, medical meetings, or scientific journals for the purposes of completing the research study, and analyzing and evaluating the results. Individual patients (subjects) will not be identified during data sharing, and a research number will be used instead during the data sharing process, unless necessary to carry out the research study or required by law.

Sample Size Determination

A priori power analysis predicting a large effect size ($F=.25$) determined that a total of 54 subjects (18 in each group), who met the inclusion and exclusion criteria will be needed, with alpha at the conventional value of .05 to achieve a .80 power, that includes an assumption of a dropout rate of 10% .

Statistical Analysis Plan

The results will be presented through the following tables with supporting explanations:

- Clinical and sociodemographic characteristics of participants by group at baseline.
- Comparisons of TUG, DGI, mCTSIB and DHI between the three intervention groups on admission and discharge.
- Comparisons of self-reported walking activity (walking MET-min/week) and total self-reported energy expenditure (total physical activity MET-min/week) as determined from the IPAQ short form on admission, discharge and four-week follow-up between the three intervention groups
- Comparisons of averages of compliance to step log recording and compliance rate for meeting step goal between the VRWP and VRW groups. Compliance is defined as low (<33%), moderate (33%-75%) and high (>75%) based on the step log or walking log. This grading of compliance was used by Hall and colleagues in their research on efficacy of gaze stability exercises in older adults with dizziness.⁵³
- Comparisons of total number of visits and length of interventions in weeks between the three intervention group.
- Intraclass Correlation Coefficients for the Timed Up and Go test-retest reliability
- Result of stepwise linear regression analysis for TUG, DGI, mCTSIB and DHI

All interval and ratio data will be tested for normality prior to undertaking the data analysis. Descriptive statistics will be used to describe the characteristics of the sample and compare the three groups at baseline. This will include Analysis of Variance (ANOVA) for parametric and Chi Square for nonparametric sociodemographic and clinical data.

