All statistical analyses were performed using SPSS version 26. Mean and standard deviation were used to describe interval and ratio data, and frequencies for nominal data. Statistical significance was set at alpha <0.05. Since the parameters of a normal distribution were not met, nonparametric statistical tests were chosen for statistical analysis.

Objective 1. To evaluate the impact of walking as an exercise component of VR on both primary and secondary vestibular-specific outcome measures.

Mean and standard deviations on the mean differences of pretest and posttest of TUG, DGI, DHI, and mCTSIB were calculated to compare walking (VRWP + VRW) and control groups (VR only). P-value was calculated using the Kruskal-Wallis test to check for between-group differences in the primary and secondary outcomes. For within-group differences, the Wilcoxon Signed Rank Test was used to examine significant differences between the pretest and posttest.

Objective 2. To evaluate whether pedometers increase the adherence of older adults with vestibular issues to a walking program.

To compare the VRWP, VRW and VR groups, IPAQ-Walk and IPAQ-Total scores were categorized as improve, same or decline in pretest and posttest, posttest and four-weeks follow-up, and pretest and four-weeks follow-up. P-value was calculated using the Kruskal-Wallis test to check for between-group differences of sociodemographic data, IPAQ-Walk, IPAQ-Total, compliance in meeting step goals and compliance in step log. Friedman's 2-way ANOVA by ranks test was used to examine significant differences within the group.

Objective 3. To establish test-retest reliability of the TUG test on older adults with dizziness.

Intraclass Correlation Coefficient (ICC) was calculated using the two-way mixed model, consistency type on a single measure model with a 95% CI for relative reliability. For absolute reliability, the Standard Error of Measurement (SEM), Minimal Detectable Change (MDC) 95% CI, and Bland-Altman 95% level of agreement were examined. The SEM provides the range of scores on retesting. A smaller value of SEM means the calculated score is close to the true score.⁴⁴ The MDC is used to reflect the true change in score that exceeded the errors of measurements. Both the SEM and MDC are the same units of the original measures, which allows easier interpretation of results when applied in the clinical practice.⁷⁴

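### Objective 2 asks VRWP v VRW on IPAQ, but the only between-group IPAQ test described is introduced as a three-arm comparison, with no pairwise estimate or CI

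*Combined protocol and SAP*

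**What the plan says.** Study Objectives gives the second purpose as finding out whether pedometers raise adherence to a walking programme. The assigned measure is change in IPAQ Walking and IPAQ Total MET-minutes/week, "compared to those patients who only received instructions to walk without a pedometer". The comparator is therefore VRW.

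The Data Analysis section, Objective 2, restates the pedometer question and then says: "To compare the VRWP, VRW and VR groups, IPAQ-Walk and IPAQ-Total scores were categorized as improve, same or decline". The between-group test follows: "P-value was calculated using the Kruskal-Wallis test to check for between-group differences of sociodemographic data, IPAQ-Walk, IPAQ-Total" (the sentence goes on to the two compliance measures). The only other test named is Friedman's: "2-way ANOVA by ranks test was used to examine significant differences within the group".

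The treatments are set out under Randomization. VRWP patients are encouraged to "increase their daily steps at least 10% until they achieve at least 3,000 steps daily". VRW patients are told to "increase their daily time at least 10% until they achieve at least 30 minutes of walking exercise daily". VR patients are treated "without the encouragement of walking and without specification of walking in the home exercise program".

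The Statistical Analysis Plan also lists an IPAQ comparison across all three groups and a repeated measures ANCOVA with group and time as factors. It names no pairwise contrast for either. Its one explicit VRWP v VRW test is for step-log and step-goal compliance.

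**The concern.** A three-arm test asks whether any arm differs from any other. The pedometer question asks whether VRWP differs from VRW. The two come apart when walking instruction works and the pedometer adds nothing: VRWP equals VRW, both exceed VR, and the three-arm null is false. A small p-value is then correct for the hypothesis tested but says nothing about pedometers. A non-significant result is no more informative, because no estimate or interval shows which pedometer effects remain plausible.

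IPAQ is the measure that the protocol assigns to this objective. As described, a significant p-value could be read as a pedometer benefit, and the report would hold no figure against which to check that reading.

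**Working it through.** **Is the contrast stated anywhere for IPAQ?**

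| Place | What it offers for IPAQ | VRWP v VRW? |
|---|---|---|
| Study Objectives | The question and comparator | Yes, as the question |
| Statistical Analysis Plan, table list | Comparison of three groups | No |
| Statistical Analysis Plan, ANCOVA | Group and time factors, no named contrast | No |
| Statistical Analysis Plan, two-tailed test | Log and goal compliance only | Not for IPAQ |
| Data Analysis, Objective 2, Kruskal-Wallis | Introduced with three arms | No |
| Data Analysis, Objective 2, Friedman | Within group | No |
| Data Analysis, Objective 4, Bonferroni | Concerns DHI severity groups | No |

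The contrast appears as a question and nowhere as an analysis.

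**The plan's own figure.** Sample Size Determination ("A priori power analysis predicting a large effect size") states f = .25, alpha .05, power .80, 10% dropout and 54 subjects. It does not state the test family, number of measurements or within-person correlation, so 54 cannot be reproduced uniquely. A group-by-time interaction with three measurements and correlation .3 needs 48, and 48/0.9 = 53.3, giving 54. A one-way comparison at f = .25 needs 159, or 177 after inflation. The point made here does not depend on which was meant.

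**How often can walking instruction alone make the three-arm test significant?** The documents give no IPAQ standard deviation or expected effect, so these inputs are assumptions:

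- 18 per arm less 10% dropout: 18 × 0.9 = 16.2, taken as 16.
- Log-normal MET-minutes, with baseline/follow-up correlation .4, .5 or .6.
- No pedometer effect: VRWP and VRW share the same walking effect over VR.
- Walking effect: for two equal arms above a third, f = d × √2/3, so f = .25 gives d = 0.25/0.471 = 0.53 SD. This reads f as a between-arm effect. A second value, 0.9 SD, shows the trend; nothing in the documents supports it.

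Proportion of simulated trials with p < .05 (4,000 per setting; ranges run over the three correlations and, in the third row, over the share of 'same'):

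| Test | 0.53 SD | 0.9 SD |
|---|---|---|
| Three-arm Kruskal-Wallis, raw change | 0.24-0.34 | 0.64-0.81 |
| Three-arm, direction of change, no 'same' | 0.19-0.26 | 0.44-0.59 |
| Three-arm, improve/same/decline, 10-30% of VR 'same' | 0.19-0.30 | 0.48-0.69 |
| VRWP v VRW ANCOVA (baseline, age) | 0.05 | 0.05 |

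With no effect in any arm, every test rejects in 0.04-0.06. With 18 per arm at 0.53 SD, raw change gives 0.27-0.37 and the three-level version 0.22-0.32. Changing the log SD from 1.0 to 0.8 or 1.2 leaves raw change at 0.24-0.34.

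**What would the direct contrast deliver?** With 16 per arm and residual SD √(1 − r²), which is 0.92 at r = .4 and 0.80 at r = .6:

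- mean 95% CI half-width 0.59-0.68 SD (simulated);
- difference detectable with 80% power 0.82-0.94 SD (noncentral t);
- power at 0.53 SD 0.35-0.44 (noncentral t).

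**The case against.** The strongest objection is that the three-arm reading is inferred. The Kruskal-Wallis sentence does not name its arms, and it also covers compliance, which the Statistical Analysis Plan compares between VRWP and VRW only. Under Objective 1 the same test follows a two-group comparison. This stands as a reason to ask which arms entered. For IPAQ, however, the sentence immediately before names all three arms and the Statistical Analysis Plan does too. On the two-arm reading there is still no stated estimate or interval.

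Second, a rejection when walking instruction works is a correct rejection, so 24-34% is not an error rate of the test. That is right. It is the chance of a significant result that has nothing to do with pedometers, and it does harm only if misattributed. No passage says it will be. Arm-level frequencies would help a reader, but they supply neither a test nor an interval.

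Third, 0.53 SD may not be the effect the trial was powered for: a one-way comparison at f = .25 has power of only about 0.30 with 48 evaluable. The effect sizes are therefore illustrative. The logical gap needs none of them.

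Fourth, Objective 2 does have a direct pedometer comparison on compliance, and the three-arm IPAQ comparison was itself planned. Both are true. They limit the point to IPAQ and make it an omission, not a departure from plan.

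Finally, a rank-based VRWP v VRW comparison with an interval would close the gap without a covariate-adjusted log-scale model. That is a fair choice of estimator and does not affect the claim.

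**Conclusion.** The concern holds. Followed as written, the analysis does not answer Objective 2 on the measure assigned to it. This rests on the text alone and applies whether categories or raw scores entered the test, which the Data Analysis section does not say. The size depends on the stated assumptions: with no pedometer effect, a 0.53 SD walking effect and 16 per arm, the three-arm test is significant in roughly a fifth to a third of trials (19-34% across outcome codings), against about 5% for the direct contrast. The gap should be fixed; it does not invalidate the three-arm results for what they test.

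**What to change.** - Name VRWP v VRW as the Objective 2 contrast for IPAQ.
- Estimate it on continuous Walking and Total MET-minutes/week, at discharge and at the four-week follow-up, adjusted for baseline IPAQ and age, with a 95% CI. Use the log scale, or a rank-based method if there are many zeros.
- State that it estimates the pedometer together with its step goal, since VRWP has a step target and VRW a time target.
- State which arms entered the Kruskal-Wallis test, and whether categories or raw scores were tested.
- Keep the three-arm test, the categories and the Friedman results as overall or descriptive.

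The cost is rewording and a re-run on data already collected. The Data Analysis section is in the past tense, so a contrast added now should be labelled post hoc. It removes walking instruction as an explanation but cannot separate the device from the step goal. Many results would be inconclusive at this sample size, so the interval, not the p-value, should carry the conclusion. If a pairwise comparison was already run, reporting it with its estimate and interval settles the point.

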The mCTSIB quantifies the ability of the patient to use information from somatosensory, visual and vestibular system effectively for postural stability. This test eliminated conditions 3 and 6 of the original CTSIB, which use an altered visual input (visual conflict dome). It is performed with the feet together, a modification from the original test, which is with feet apart.⁵¹ The four conditions of mCTSIB are standing on firm surface eyes open, standing on firm surface eyes closed, standing on compliant surface eyes open, and standing on compliant surface eyes closed. The patient is timed for 30 seconds and the average score of three trials is obtained. It only requires a timer and balance foam to administer the test. It has been found to have good agreement (kappa values 0.53-0.81) between two testers and is considered as a less costly alternative to computerized analysis of balance.³⁶ There is no established MDC and MCID on mCTSIB for older adults with dizziness.

The IPAQ short form is an instrument evaluation tool of physical activity among the adults. It has three categories: low, moderate and high. The specific type of activities assessed are walking, moderate intensity activities and vigorous intensity activities. All continuous scores are expressed in MET-minutes/week with walking =3.3 METs, Moderate PA=4.0 METs and Vigorous PA = 8.0 METs. An overall total physical activity score can be computed as the sum of the total MET-minutes/week scores.²³ This outcome measure will be used to compare the pre- and post-intervention physical activity level of the participants. The total time walked per week item of the IPAQ short form has a test-retest reliability of 0.72 using Spearman Correlation.⁵²

Data Management and Quality Plan

Data De-identification

Each subject will be assigned a research number for data de-identification. The research number is based on the randomization list generated by the online randomization program (<https://www.sealedenvelope.com/simple-randomiser/v1/lists>). The list of names with corresponding research numbers will be kept in a locked cabinet in Florida Hospital and password protected Florida Hospital computer by the study coordinator

Data Confidentiality, Storage, and Retention

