Analyses will employ five repeated measures Analysis of Covariance (ANCOVA), adjusting for age, with two independent variables (group and time) and five outcome measures (TUG, DGI, DHI, mCTSIB and IPAQ short form). The adjustment of age is based on age-related decline. Intraclass Correlation Coefficient will be calculated to establish the test-retest reliability of the TUG and a stepwise linear regression with age as covariate will be conducted for all 54 subjects at baseline to determine if TUG, mCTSIB and DGI are predictors of DHI. Two-tailed test will be utilized to compare the compliance with step log recording and meeting step goals between the two walking groups (VRWP and VRW), and ANOVA to compare of total number of visits and total length of intervention in weeks between the three groups. Alpha for all analyses will be set at 0.05 to test for significant difference.

Potential Risks and Benefits

Potential Benefits

Possible benefits include improved physical function.

Potential Risks

The addition of a prescribed walking program in the treatment of dizziness will challenge the subject's balance, and in rare cases may result in falls or more dizziness.

Performance-based outcomes such as mCTSIB, DGI, and TUG check for the subject's reaction whenever in a condition of unsteadiness. The risks associated with these tests are the potential for falls and for dizziness. Self-report questionnaires such as the DHI and IPAQ will need the subject to read the questions and recall past experiences. Looking down and reading the questions may provoke dizziness and eye strain. Other possible risks for subjects are: 1) finding the questions to be sensitive 2) emotional discomfort (uncomfortable/embarrassed/sad/tired) and 3) distress as subject thinks of experiences.

Mitigation of Risks

The research staff (treating physical therapist) will supervise the treatment at all times to minimize any such risks.

Provisions to Protect the Privacy Interest of Subjects

Subjects will be assigned research numbers for study-related records and data sharing. The patient's confidentiality will be protected by observing the HIPAA policies and procedures.

Early Withdrawal of Subjects

Investigator Withdrawal of Subjects

The PI may terminate the participation of the subject in the study if the subject may be in any danger or no longer meets the inclusion criteria of the study.

Subject Request for Withdrawal from Study

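### Objective 2 is defined as change in IPAQ MET-minutes/week, but the arms are compared through improve/same/decline classes with no cut-off, no stated test variable and no between-arm estimate of change

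*Combined protocol and SAP*

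**What the plan says.** Four sections treat the IPAQ result as a quantity. Study Objectives measures the second purpose by "change in physical activity, as represented by International Physical Activity Questionnaire (IPAQ) Walking Metabolic Equivalent of Task (MET)-minutes/week", together with the corresponding total score, and contrasts pedometer users with patients told to walk without one. Study Outcome Measures (Endpoints) states: "All continuous scores are expressed in MET-minutes/week". The Statistical Analysis Plan section promises "Comparisons of self-reported walking activity (walking MET-min/week) and total self-reported energy expenditure" by arm at admission, discharge and four weeks. It also lists the IPAQ among the outcomes for repeated measures ANCOVA.

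The later Data Analysis section reports that normality was not met and that nonparametric tests were chosen. Under Objective 2, with the declared aim of comparing the three arms, it then says: "IPAQ-Walk and IPAQ-Total scores were categorized as improve, same or decline in pretest and posttest". The same is done for posttest to four weeks and for pretest to four weeks. The next sentence names Kruskal-Wallis for IPAQ-Walk and IPAQ-Total without saying in what form they enter. Friedman's test is used within groups.

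Neither section gives a minimum change, a band for 'same', or an MDC or MCID for the IPAQ.

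**The concern.** The endpoint as defined asks how much more people walk. Three ordered classes record only the direction of change, and the rule that assigns them is not written down, so another analyst could not reproduce the comparison.

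Non-normality does not explain the step. It is a reason to use ranks, and Kruskal-Wallis can rank the changes themselves. Under the same non-normality, Objective 1 still reports means and SDs of the pre-to-post differences, and Objective 3 uses an MDC to separate real change from measurement error. Objective 2 specifies neither.

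At stake is whether a comparison with 18 people per arm can detect a pedometer effect, and whether it can say how large that effect is.

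**Working it through.** The plan has no figure of its own to reproduce here. Sample Size Determination gives 54 participants (18 per arm), but no IPAQ SD and no target difference in MET-minutes. Only the 18 per arm is used below.

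**1. What one class can contain.** Walking is weighted at 3.3 METs (Study Outcome Measures).
- One extra 10-minute walk a week: 3.3 × 10 = 33 MET-minutes/week.
- Thirty extra minutes a day (the VRW walking goal, used only as an illustration): 3.3 × 30 × 7 = 693 MET-minutes/week.
- Ratio: 693 / 33 = 21. If 'same' means unchanged, both are 'improve'.

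**2. How recall error is classed.** The only reliability given is "The total time walked per week item of the IPAQ short form has a test-retest reliability of 0.72 using Spearman Correlation". Treating 0.72 as a test-retest correlation with normal errors (an assumption):
- SD of the difference when nothing has changed = √(2 × (1 − 0.72)) = 0.75 between-person SDs.
- 95% detectable change = 1.96 × 0.748 = 1.47 SDs.
- P(classed 'improve' | no true change) = 1 − Φ(c / 0.748) for cut-off c. This is 50% at c = 0, 25% at c = 0.5 SD and 2.5% at c = 1.47 SD.

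The 50% falls if exact ties, such as zero walking both times, are common. The documents give no tie rate.

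**3. Power.** Simulation with three arms of 18, one arm shifted, alpha 0.05 and 10,000 trials per setting. Kruskal-Wallis was run on the changes and on their sign. Shifts and drift are assumptions. Entries are power on changes versus power on classes, in percent.

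| Changes | Common drift | Shift 0.5 | Shift 0.8 | Shift 1.0 |
|---|---|---|---|---|
| Normal | 0 | 29 vs 19 | 63 vs 41 | 84 vs 58 |
| Normal | 0.3 | 28 vs 16 | 65 vs 36 | 84 vs 49 |
| t, 3 df | 0 | 20 vs 16 | 45 vs 33 | 63 vs 46 |
| t, 3 df | 0.3 | 20 vs 14 | 44 vs 27 | 63 vs 36 |

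The loss runs from 10 (29 − 19) to 35 (84 − 49) points for normal changes, and from 4 (20 − 16) to 27 (63 − 36) for t3. Shorter runs move these by a point or two. For the normal rows the unit is one SD of change. For t3 it is the scale of the distribution, whose SD is √3 = 1.73, so those shifts are 0.29 to 0.58 SD. With no shift, both versions reject in 4% to 5% of trials.

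**4. A graded effect and a band.** With VRWP shifted by 1.0, VRW by 0.5 and VR by 0 (4,000 trials), power on changes versus classes is 71% versus 48% for normal changes and 52% versus 37% for t3. A 'same' band of ±0.5 units raises the class version to 61% and 47%, so a stated cut-off recovers part of the loss.

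**The case against.** The strongest reply is that the Data Analysis text does not say the classes were what was tested. Classification is in one sentence and Kruskal-Wallis in the next, where the variables carry the names of the scores. The general rule in that section gives mean and SD for ratio data, the protocol's planned tables show MET-minutes/week by arm and time, and Friedman's test most naturally ranks the scores. A reader might therefore infer too much in concluding that the size of any walking increase is lost altogether, or that trivial shifts are known to have counted as success. The documents support neither. The first ignores those descriptive provisions. The second requires 'same' to mean exactly equal, and no rule is given. If the classes instead meant moves between the IPAQ low, moderate and high levels, most people might be 'same', and the documents describe no such levels for walking alone.

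The numerical side also has limits. The 0.72 is a Spearman value for one walking item, not for IPAQ-Total, and recall error affects the continuous change as well. The shifts are hypothetical.

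All of this stands, and it makes the consequences conditional. It does not settle the matter. The classifying sentence opens with the comparison of arms as its purpose. A test on scores at a single time point would not address the change the objective defines. A within-group test cannot compare pedometer with no pedometer. On every reading, the class rule, the test variable and a between-arm estimate are missing.

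**Conclusion.** The point holds in this form: Objective 2's endpoint is a continuous change, while its between-arm analysis is described through three undefined classes, with the test variable unstated and no between-arm estimate of MET-minute change named.

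If the classes were tested with no band, the cost is the magnitude of change in that comparison plus a loss of power of about 10 to 35 points (normal changes) or 4 to 27 points (t3). This assumes 18 per arm, one arm shifted by 0.5 to 1.0 units, and a common drift of 0 or 0.3. The size cannot be fixed more closely without an IPAQ SD. If changes in MET-minutes/week were in fact ranked, there is no power loss, and the defect is one of reporting and of the missing estimate.

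A reader might also infer that the classes inflate false positives. The simulation with no shift gives no sign of that.

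**What to change.** - State that the tested variable is change in IPAQ-Walk and in IPAQ-Total MET-minutes/week, for each of the three intervals, using the Kruskal-Wallis test already named.
- Report median change and IQR per arm.
- Report the VRWP-versus-VRW difference in change with a 95% CI, for example Hodges-Lehmann. The three-arm test alone does not isolate the pedometer question posed in Study Objectives.
- Keep improve/same/decline as a descriptive table, with the cut-off for 'same' stated and justified.

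The scores are already collected, so the cost is a small re-analysis and revised wording. The Data Analysis section is written in the past tense. If results have been seen, the re-analysis should be labelled post hoc and shown beside what was done.
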